# 2. Background

## 2.1 Introduction and state of research

Von Willebrand Disease (VWD) is the most common inherent bleeding disorder [1]. The disease is caused by deficiency or dysfunction of von Willebrand factor (VWF), a plasma protein that mediates platelet hemostatic function and stabilizes blood coagulation factor VIII. VWF is also the carrier of factor VIII in plasma. Thus, its deficiency may also result in low levels of factor VIII.

Estimates for prevalence of VWD range between 0.6 and 1.3% [2]. Inherent VWD is classified into three main types (1, 2 and 3) with type 2 divided into four subtypes (A, B, M, N) [3]. The most prevalent and mildest form is VWD type 1 (about 75%) representing a partial quantitative deficiency of VWF [1]. VWD type 2 (qualitative defects of VWF) accounts for around 20 to 25% of cases [1]. Subtype 2A exhibits impaired VWF multimer assembly (group 1 mutations) or increased proteolysis of VWF in circulation (group 2 mutations). Subtype 2B shows increased, type 2M decreased affinity of VWF for platelet GPIb receptor. Subtype 2N is characterized by decreased factor VIII because of VWF deficiently binding to factor VIII [1]. VWD type 3 (0.6 to 6% of cases) represents complete quantitative deficiency of VWF [1, 3, 4]. These three major types of VWD may affect both males and females. Type 1 and type 2A and 2B are inherited in an autosomal dominant manner while type 2M, 2N and 3 are inherited in an autosomal recessive manner [3].

People with VWD bruise easily, have recurrent mucocutaneous bleeding, or bleed after tooth extraction, tonsillectomy or other surgery [5]. A common symptom of VWD is epistaxis (nose bleeding). Furthermore, women can have increased menstrual bleeding. Also a frequently reported symptom of VWD is gingival bleeding [6-8].

Gingival bleeding is also a leading symptom of plaque-induced gingivitis and untreated periodontal disease [4, 9, 10]. Interestingly case reports on VWD reporting spontaneous gingival bleeding as symptom did not look into periodontal health in detail. Abbas & Prabhu report "fair oral hygiene" and the gingival tissues to "look otherwise healthy" [6]. In another case continual bleeding 12 hours after scaling and polishing of the lower teeth is reported [8]. However, plaque indices or periodontal

[name] & [name] (143/15: Version 2: 27.05.2015)

variables as probing pocket depths (PPD) and vertical probing attachment level (PAL-V) [6, 8].

# 2.2 Previous work

A case control study comparing type 1 VWD with controls matched for sex, age, number of teeth, severity of periodontal disease, and smoking failed to detect increased gingival bleeding in VWD [4].

## 3. Aim

#### 3.1 Hypothesis

The sypmtome gingival bleeding in patients suffering from VWD type 2 and 3 is not primarily due to VWD but due to inflammatory periodontal diseases (gingivitis, periodontitis).

#### 3.2 Aim of the study,

assessment whether in patients suffering from VWD type 2 and 3 the regularly occuring symptome gingival bleeding is caused by the impaired coagulation due to VWD or due to inflammatory periodontal diseases (gingivitis, periodontitis).

If patients are diagnosed with gingivitis or periodontitis patients who want so may have periodontal treatment at the Dept. of Periodontology.

## 4. Outcomes

#### Primary outcome (bleeding symptome):

- BOP (Bleeding on probing)

#### Secondary outcome:

- GBI (Gingival Bleeding Index) (Ainamo & Bay 1975)

#### **Control variables:**

- PCR (Plaque Control Record) (O'Leary 1972)
- Probing pocket depths (PPD)

[name] & [name] (143/15: Version 2: 27.05.2015)

# 5. Material and Methods

# 5.1 Test (VWD patients)

In the present prospective case control study patients suffering from type 2 and 3 VWD (VWF Ristocetin cofactor [VWF:RCo] < 30%) were compared to hematologically healthy controls matched for sex, age, number of teeth, severity of periodontal disease, and smoking.

This study applies the protocol of a case control study comparing type 1 VWD with controls matched for sex, age, number of teeth, severity of periodontal disease, and smoking to type 2 and 3 VWD patients [4]. All patients with type 2 and 3 VWD consecutively consulting the Haemophilia Centre, Medical Clinic II/Institute for Transfusion medicine, Hospital of the Johann Wolfgang Goethe-University Frankfurt/Main were asked to participate in this study as cases. They were asked for bleeding and subjective symptoms indicating periodontal disease. This study is a human observational study and conforms to the STROBE guidelines.

The study complied with the rules of the Declaration of Helsinki and was approved by the Institutional Review Board for Human Studies of the Medical Faculty of the Goethe-University Frankfurt/Main (Application# 143/15). All participating individuals were informed on risks and benefits as well as the procedures of the study and gave written informed consent. The study is registered under the number NCT03078595 at http://www.clinicaltrials.gov.

## Inclusion criteria:

- Age between 18 and 80 years,
- Written informed consent,
- Formerly diagnosed type 2 and 3 VWD (according to VWF multimer analysis and VWF:RCo < 30 %)

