## **Exclusion criteria:**

- Requirement of systemic antibiotics for measures that may cause transitory bacteremia (e.g. pocket probing),
- VWD type 1 (VWF:RCo > 30 %),
- Additional bleeding disorders (e.g. hemophilia A or B),
- Anticoagulation or antiplatelet treatment (e.g. acetylsalicylic acid, warfarin)

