# 5.5 Hematologic examinations

Twenty ml of blood was sampled from an arm vein. The following data were assessed at the Haemophilia Centre for clinical routine during VWD patient care and due to study design as well as to determine whether haemotological disease was present or not in the controls:

- von Willebrand parameters (VWF antigen [VWF:Ag], VWF activity [VWF:Act], coagulation factor VIII [FVIII:C])
- Current medication if any

Also diabetes mellitus and glycemic control may interfere with systemic as well as periodontal inflammation and, hence, gingival bleeding [14, 15]. Even so called prediabetes may contribute to inflammation. However, the state of prediabetes may not be known by the affected individual and not detected by medical history [15]. Thus, HbA1c as a measure for glycemic control was assessed also.

VWF:Ag and VWF:Act were measured turbidimetrically using a BCS (Siemens, Marburg, Germany). FVIII:C was assessed with specific agents on a coagulation analyzer (ACL-700®, IL Instrumentation Laboratory, Kirchheim, Germany).

[name] & [name] (143/15: Version 2: 27.05.2015)

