In all individuals hematological and periodontal examinations were obtained within 24 hours. After dental and periodontal examination all patients received oral hygiene instructions and professional tooth cleaning. In cases of untreated periodontal disease periodontal treatment was offered. Increased bleeding may occur at home after patients had already left the clinic. Thus, only subjects with VWD were asked to

[name] & [name] (143/15: Version 2: 27.05.2015)

report any bleeding complications after periodontal probing and professional tooth cleaning.

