# 5.7 Statistical analysis

The individual patient was used as statistical unit. All analyses were performed on patient level. BOP was defined as the main outcome variable and GBI as secondary outcome variable. All other parameters were control variables.

For all individuals, cigarette pack years were calculated. Group frequencies (VWD, control) were expressed for sex, current smoking. Group means and standard deviations were calculated for GBI, BOP, age, number of remaining teeth, pack years, CO, PCR, Body weight, VWF:Ag, VWF:RCO, FVIII:C, Hb1c. Further, for each individual the following variables were calculated to describe the periodontal status:

- Mean±standard deviation of PPD and PAL-V
- Percentage of PPD < 4 mm, 4 to 6.8 mm, ≥ 7 mm
- Sum of all PPD (Wohlfeil et al. 2009), i.e. the sum the PPD measured at all sites within a patient
- Sum of all PPD with BOP (Wohlfeil et al. 2009), i.e. the sum the PPD measured at all sites exhibiting BOP within a patient
- Periodontal inflamed surface area (PISA) [20, 21]. For each patient PPD were entered into an Excel sheet that can be downloaded freely (http://www.parsprototo.info/pisa.html).

From these group means and standard deviations were calculated. Comparisons between groups for dichotomous parameters were made by  $\chi^2$  or Fisher's exact test and for all other parameters by Mann-Whitney-U test. A post-hoc analysis was performed to estimate the test power that would be required to find a clinically relevant inter-group difference ( $\delta$ ) of 5.5% for BOP and GBI index with a type 1 error ( $\alpha$ ) of 0.05 for the actual sample size.

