Using stepwise linear backward multiple regression analysis, factors should be identified that influenced BOP and GBI. The following independent variables were entered into the model for BOP: group (VWD/control), VWD type 2 or 3, sex, age, body weight, HbA1c, PCR, CO, aMMP-8, number of remaining teeth, PISA. The following independent variables were entered into the model for GBI: group (VWD/control), VWD type 2 or 3, sex, age, body weight, HbA1c, PCR, CO, aMMP-8, number of remaining teeth, PISA. Due to the fact that mean PPD is mathematically coupled to sum of PPD, sum of PPD with BOP, and PISA these 4 variables were not entered into the regression model at the same time. PISA provides the best representation of the subgingival inflamed area. Thus, PISA was chosen for the final model. The following parameters were described by dummy variables: group (control = 0, VWD = 1), sex (male = 0, female = 1), smoking status (never and former smoker = 0, current smoker = 1). All factors with p < 0.05 were kept in the models. For statistical analysis a PC program was used (SystatTM for Windows Version 13, Systat Inc., Evanston, USA).

[name] & [name] (143/15: Version 2: 27.05.2015)

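### VWF activity, FVIII and medication are recorded within 24 hours of probing but enter no BOP or GBI analysis, so the plan neither tests the proposed cause directly nor checks whether treated cases could dilute the group difference

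*Combined protocol and SAP*

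**What the plan says.** The aim (section 3.2) is to decide whether gingival bleeding in type 2 and 3 VWD comes from impaired coagulation or from inflammatory periodontal disease. The hypothesis (section 3.1) is that VWD is not the main cause.

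- **Entry.** Cases qualify as "Formerly diagnosed type 2 and 3 VWD"; with its basis, the inclusion criterion reads "Formerly diagnosed type 2 and 3 VWD (according to VWF multimer analysis and VWF:RCo < 30" per cent. No value at the study examination is required. The only exclusion by drug effect on bleeding is "Anticoagulation or antiplatelet treatment (e.g. acetylsalicylic acid, warfarin"); treatment that raises VWF or FVIII is not addressed.
- **Measurement.** Section 5.5 lists "von Willebrand parameters (VWF antigen [VWF:Ag], VWF activity [VWF:Act], coagulation factor VIII [FVIII:C"]) and "Current medication if any". Section 5.6 adds: "In all individuals hematological and periodontal examinations were obtained within 24 hours".
- **Analysis.** Section 5.7 gives group means and standard deviations for a list that includes "VWF:Ag, VWF:RCO, FVIII:C, Hb1c", and compares non-dichotomous parameters by Mann-Whitney U test. The backward regressions for BOP and for GBI start from the same set: "group (VWD/control), VWD type 2 or 3, sex, age, body weight, HbA1c, PCR, CO, aMMP-8, number of remaining teeth, PISA". Neither contains a VWF, FVIII or medication term.

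**The concern.** The study measures the proposed cause close in time to the outcome and then leaves it out of every outcome model, although HbA1c, exhaled CO and body weight are included. Two things follow.

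First, the most direct question the data can address, whether lower measured VWF activity goes with more bleeding at equal plaque, is not asked.

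Second, group membership is a diagnostic label. A case whose haemostasis had been raised by treatment when probed would still count as fully exposed. Such cases would pull the difference between VWD and control toward zero. Because the hypothesis predicts little or no difference, that error would favour it. The study was also analysed with 24 pairs where 31 were planned, so a null result is already weak evidence.

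**Working it through.** **1. What the planned analyses can show**

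| Item | Collected (5.5, 5.6) | Summarised or compared by group (5.7) | In a BOP or GBI model (5.7) |
|---|---|---|---|
| VWF:Ag | yes | yes | no |
| VWF:Act | yes | not under this name; VWF:RCO is listed | no |
| FVIII:C | yes | yes | no |
| Current medication | yes | not named | no |
| Group, VWD type | yes | group defines the comparison | yes |

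**2. The plan's own sample size**

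Inputs from section 5.3: 31 per group, difference 5.5 points, alpha 0.05, power 80%. No SD is given, so the figure cannot be reproduced forward; it can only be solved for the SD. I assume a two-sided test, since sidedness is not stated.

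- t-test, 80% power at n = 31 per group: SD = 7.60.
- Normal approximation: SD = 5.5 / [(1.960 + 0.842) × √(2/31)] = 7.73.
- If one-sided: 8.61 (t-test) or 8.71 (normal).

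At 24 per group, the two-sided t-test with SD 7.60 has noncentrality 5.5 / (7.60 × √(2/24)) = 2.51 and power 69%. The one-sided reading gives 70%. The fall from 80% to 69% comes from recruitment alone, not from how exposure is defined.

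**3. Illustration of dilution**

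Suppose k of the 24 cases had no VWD effect on bleeding when probed, the others had the full effect, and the SD is unchanged. The expected difference is 5.5 × (1 − k/24). The documents give no k; the range is an assumption.

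| k | Expected difference (points) | Power at 24 + 24, SD 7.60 |
|---|---|---|
| 0 | 5.50 | 69% |
| 2 | 5.04 | 61% |
| 4 | 4.58 | 53% |
| 6 | 4.13 | 45% |
| 8 | 3.67 | 37% |

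**4. What a within-case analysis could detect**

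Fisher z, two-sided alpha 0.05, n = 24: power = Φ(atanh(r) × √(n − 3) − 1.96).

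- r = 0.55: 0.618 × √21 = 2.83, power 81%. With one covariate (√20), 79%.
- r = 0.30: 0.310 × √21 = 1.42, power 29%.

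Only a strong association would be found reliably.

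**The case against.** **A former diagnosis is not a stale one.** Section 2.1 describes VWD types 2 and 3 as inherited qualitative defects or complete deficiency. A diagnosis made by multimer analysis and VWF:RCo does not lapse. This stands: the entry criterion is not itself the defect, and only something transient, such as treatment, could create the problem.

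**No case is shown to have been treated.** This also stands. A reader might infer from the wording of the criterion that non-deficient cases were enrolled and that the result is biased toward the hypothesis. The documents support only that the criteria would allow it and that no planned outcome analysis would check it. Equally, the type 1 exclusion (VWF:RCo above 30%) does not rule it out: it reads as a definition of type 1 rather than a screen at the examination, and section 5.5 does not list VWF:RCo among the study measurements.

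**The levels are used.** They are compared between groups as well as tabulated, and this would show whether cases were low on the whole. VWD type in the regression is a coarse contrast of severity. Both points are fair. But a group comparison does not identify individual cases or relate level to bleeding, and type is not status at probing.

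**The additions have limits.** The 30% limit is set for VWF:RCo and cannot simply be carried over to VWF:Act. Activity is not a uniform scale of severity across subtypes: section 2.1 defines 2N by deficient factor VIII binding. A sample within 24 hours, with no order stated, may not give the level at the moment of probing. Removing medicated cases may remove the most severe disease and itself push toward the null. If all cases have low activity, the narrow range weakens the within-case analysis further. These points shape the fix and confine it to a supportive role.

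**Conclusion.** The concern holds as a missed analysis and an unchecked possibility. The plan collects coagulation status and medication close to probing, but no BOP or GBI analysis uses them, although the aim is about impaired coagulation. If some cases were not deficient when probed, the bias would run toward the null; whether and how often this occurred is unknown.

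The figures of 5.0 to 3.7 points and 61% to 37% power are illustrations. They rest on an assumed 2 to 8 cases, an all-or-nothing effect, and an SD that the protocol does not state. They should not be read as an estimate of bias in this study.

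No planned analysis is made invalid by this. The gain is a more direct answer to the stated aim, and a null result that is easier to interpret, from data already in hand. Separately, section 5.5 measures VWF:Act while section 5.7 summarises VWF:RCO, so the tabulated variable cannot be traced to the measured one.

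**What to change.** In section 5.7:

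1. Add a supportive analysis within cases: BOP and GBI on measured VWF:Act, and on FVIII:C, adjusted for PCR. Report estimates with confidence intervals. State that with 24 cases a correlation of about 0.55 is needed for 80% power and that power at 0.30 is about 29%, so a null is not evidence of no effect.
2. Report how many cases had raised activity, or recorded VWF-raising or haemostatic medication, at the examination. Add a supportive sensitivity comparison without those pairs. Define the activity limit for the assay actually measured, and note that the restriction may remove severe cases.
3. Reconcile VWF:Act in section 5.5 with VWF:RCO in section 5.7, and state which assay produced the reported values.

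The cost is two small, imprecise supportive analyses, one count and one correction to the text. No new data, recruitment or change to patient care is needed.

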## **Exclusion criteria:**

- Requirement of systemic antibiotics for measures that may cause transitory bacteremia (e.g. pocket probing),
- VWD type 1 (VWF:RCo > 30 %),
- Additional bleeding disorders (e.g. hemophilia A or B),
- Anticoagulation or antiplatelet treatment (e.g. acetylsalicylic acid, warfarin)

# 5.2 Controls

For each case (VWD) a respective hematologically healthy control was recruited from the gingivitis and periodontitis patients of the Department of Periodontology, Center for Dentistry and Oral Medicine (Carolinum), Johann Wolfgang Goethe-University Frankfurt/Main. Each control was matched to one of the respective cases for sex, age (±5 years), self-reported smoking status (current smoker/non-smoker), number of

[name] & [name] (143/15: Version 2: 27.05.2015)

remaining teeth (±2 teeth), and periodontal diagnosis (gingivitis, chronic or aggressive periodontitis).

Smoking may interfere with gingival bleeding [11, 12]. Thus, all participants were asked about current and past cigarette smoking habits. Patients who reported smoking or had quit smoking for less than five years were classified as smokers [13]. Additionally the amount of carbon monoxide (CO) in exhaled air was measured using a Smokerlyzer® (Bedfont Smokerlyzer EC50-Micro; Bedfont Scientific Ltd, Rochester, Great Britain).

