# 5.3 Fallzahlschätzung

A sample size of n = 62 (31 VWD cases and 31 controls) was required to detect an inter-group difference of 5.5% [4] GBI or BOP with a type 1 error  $\alpha$  < 0.05 and a test power of 80% (http://jumbo.uni-muenster.de/fileadmin/jumbo/applets/falla.html). After inclusion of 24 type 2 and 3 VWD cases no further type 2 and 3 VWD cases could be recruited at the Haemophilia Centre, Medical Clinic III/Institute for Transfusion medicine, Hospital of the Johann Wolfgang Goethe-University Frankfurt/Main. Thus, the study was analyses with 24 cases and 24 matched controls.

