# 5.6 Periodontal examinations

For all participants, a commercially available test (PerioSafe®, Dentagnostics, Jena, Germany) was performed to detect activated matrix metalloproteinase 8 (aMMP-8) from the gingival sulcus. First, patients rinsed with tap water for 30 seconds then spat the water out. After 1 minute, the patients rinsed with 5mL of purified water for 30 seconds and spat the sample back into the test cup. A syringe was used to gather 2mL of the sampled saliva and water mixture. A filter was then put onto the syringe and 3 drops of the saliva was pressed through the filter into the ELISA kit. After 5-10 minutes, the result was read from the test kit [16]. If both the control and test strips were visible ( $\geq$  25 ng aMMP 8 per mL), the respective test was positive.

The following clinical parameters were assessed at 6 sites per tooth (mesiobuccal, buccal, distobuccal, mesiolingual, lingual, distolingual) [4]:

- modified Gingival Bleeding Index (GBI) [17]
- modified Plaque Control Record (PCR) [18]
- PPD and recession to the nearest 0.2 mm using an electronic probe (Florida Probe, Version 3.2, Gainesville, FL, USA). Recession was assessed from the cemento-enamel junction (CEJ) to the gingival margin. At sites where the CEJ was destroyed by restorations the restoration margin (RM) was used as reference. At sites where the CEJ or RM was located apically from the gingival margin the value for recession was negative
- Bleeding on probing (BOP) recorded as positive when bleeding occurred within 30 seconds from probing. For each patient a BOP index was calculated providing the amount of sites with positive BOP in % per patient.
- Attachment loss was calculated as sum of PPD and recession. At sites where the gingival margin was located coronally of the CEJ recession was scored as a negative value.

All individuals were classified into the following diagnoses [14, 19]:

- plaque-induced gingivitis (PPD < 3.6 mm; PAL-V  $\leq$  2 mm),
- generalized mild, localized moderate chronic periodontitis (PPD ≥ 3.6 mm; PAL-V 3 to 4 mm ≤ 30% of sites; 1 to 2 mm > 30% of sites),
- generalized mild, localized severe chronic periodontitis (PPD ≥ 3.6 mm; PAL-V ≥ 5 mm ≤ 30% of sites; 1 to 2 mm > 30% of sites)
- generalized moderate chronic periodontitis (PPD ≥ 3.6 mm; PAL-V 3 to 4 mm > 30%)
- generalized moderate localized severe chronic periodontitis (PPD ≥ 3.6 mm; PAL-V 3 to 4 mm > 30%; ≥ 5 mm ≤ 30%)

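### No planned analysis is guaranteed to report a severity-adjusted VWD minus control difference in BOP, and the matching text leaves open whether severity was controlled by design

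*Combined protocol and SAP*

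**What the plan says.** Section 3.2 sets the question: whether gingival bleeding in type 2 and 3 VWD "is caused by the impaired coagulation due to VWD or due to inflammatory periodontal diseases". BOP is the primary outcome.

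**Matching.**
- Section 5.1 says that cases "were compared to hematologically healthy controls matched for sex, age, number of teeth, severity of periodontal disease, and smoking".
- Section 5.2 gives the working rule. Controls were "recruited from the gingivitis and periodontitis patients of the Department of Periodontology" and matched on sex, age within 5 years, smoking status, "remaining teeth (±2 teeth), and periodontal diagnosis (gingivitis, chronic or aggressive periodontitis". No tolerance on pocket depth (PPD) or attachment level (PAL-V) is given.
- Section 5.6 states that "All individuals were classified into the following diagnoses", then lists gingivitis and four grades of chronic periodontitis, the last being "generalized moderate localized severe chronic periodontitis". It has no aggressive class.

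**Analysis (section 5.7).**
- Continuous measures, BOP included, are compared between groups by Mann-Whitney test.
- Group means and SDs are given for PPD, PAL-V and PISA.
- A backward stepwise linear model for BOP starts from 11 candidates, with group and PISA among them. PISA is preferred to three other pocket-depth measures because the four are mathematically coupled. Factors stay only if p < 0.05.

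Section 4 lists "Probing pocket depths (PPD") and plaque (PCR) as control variables. Section 5.3 reports that "the study was analyses with 24 cases and 24 matched controls", against 31 per group planned.

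**The concern.** Cases come from a haemophilia centre and controls from a periodontology department. The groups could therefore differ in severity of periodontal disease, in either direction. The quantity that answers section 3.2 is the VWD minus control difference in BOP at equal severity, with an interval to compare with 5.5 points.

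The Mann-Whitney test does not adjust for severity. The regression adjusts only while its terms survive, and group, the exposure of interest, has no protection. The hypothesis in section 3.1 is that VWD is not the primary cause. If that is true, group is likely to be dropped, and the report could then say that group was not significant without showing which differences the data exclude.

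Sound matching on severity would make this matter less, but the text does not establish that grade was matched.

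**Working it through.** **1. Matching text side by side.** Section 5.1 names severity as a matching factor. Section 5.2 names three classes without grades. Section 5.6 has five classes, four of them grades of chronic periodontitis. Read literally, section 5.2 lets any chronic grade be paired with any other. Section 5.6 also calls its grades diagnoses, so the bracket in 5.2 may stand for them. The lists do not map onto each other, because aggressive periodontitis is in 5.2 only. The text does not settle whether grade was matched.

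**2. What section 5.7 guarantees.**

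| Analysis | Group effect always reported? | Severity always adjusted for? |
|---|---|---|
| Mann-Whitney on BOP | yes, as a test | no |
| Backward model, at the start | group is a candidate | PISA is a candidate |
| Backward model, at the end | only if p < 0.05 | only if p < 0.05 |

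The remark that PISA was chosen for the final model reads as a choice among four coupled measures. Even if it means that PISA always stays, group still need not.

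**3. How often group could be dropped (illustration).** Backward elimination was simulated with 24 + 24 patients, 11 candidates, a p < 0.05 rule and 1,000 runs per scenario. All inputs are assumptions: residual SD 7.73, severity worth 2 or 4 BOP points per SD, controls 0, 0.5 or 1 SD more severe, 5 cases of the second VWD type, and eight pure-noise candidates.
- True difference 5.5 points: group kept in 50–67% of runs, group and severity both kept in 25–60%.
- True difference 0: group kept in 6–10% of runs.

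**4. SD for the cost calculation.** The plan gives no SD. Solving its own design (31 per group, difference 5.5, two-sided alpha 0.05, power 80%, t-test assumed) gives a standardized difference of 0.723, so SD = 5.5 / 0.723 = 7.6. This is an assumption.

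**5. Precision of the adjusted difference.** Half-width = t × SD × √(2/24) × √VIF, where 7.6 × √(2/24) = 2.194. For covariates whose group means differ by d within-group SDs, with within-group correlation matrix R, VIF ≈ 1 + d′R⁻¹d / 4. No gain from explained variance is counted.

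| Model | df, t | VIF | Half-width | Ratio to unadjusted |
|---|---|---|---|---|
| Unadjusted | 46, 2.013 | 1 | 4.42 | 1 |
| One covariate, 0.5 SD apart | 45, 2.014 | 1.0625 | 4.55 | 1.03 |
| Two, each 0.5 SD apart, r = 0 | 44, 2.015 | 1.125 | 4.69 | 1.06 |
| Two, r = 0.5, same direction | 44, 2.015 | 1.083 | 4.60 | 1.04 |
| Two, r = 0.5, opposite directions | 44, 2.015 | 1.25 | 4.94 | 1.12 |

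The last row: d′R⁻¹d = 2 × 0.25 × 1.5 / 0.75 = 1.0, so VIF = 1 + 1.0/4 = 1.25.

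**6. Does a non-significant severity comparison settle the matter?** With 24 per group, one unpaired t-test has 40% power to show a 0.5 SD imbalance and 77% at 0.8 SD (Mann-Whitney with normal data: 38% and 75%). This describes a single unpaired test. The plan reports several severity measures with means and SDs, so it carries limited weight.

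**The case against.** **Severity is already in the plan.** This is true in part. PPD, PAL-V and PISA are described and compared by group, so a reader can see an imbalance whatever its p-value. Group is first tested with PISA in the model, so dropping group while PISA remains is the result of an adjusted test. A reader might infer that severity is missing from the analysis, or that only the unadjusted comparison would be left. The documents support neither. What is missing is a guaranteed adjusted estimate with its interval.

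**The matching discrepancy may be loose wording.** This also stands. A reader might infer that controls were not matched on severity. Sections 5.2 and 5.6 do not show that. They only fail to show the opposite, which calls for clearer wording and a table.

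**No bias is demonstrated.** Correct. As algebra only, the shift in the BOP difference equals imbalance in SD × within-group correlation with BOP × SD of BOP. At 0.5 SD and SD 7.6 it is 0, 1.1 or 1.9 points for correlations of 0, 0.3 or 0.5, in either direction. The documents give none of these inputs.

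**The smallest repair would force in group and PISA, the plan's own choice.** This is a fair alternative. PAL-V is proposed because, with PPD, it defines the section 5.6 diagnoses and so the severity that matching was meant to control. The documents do not show PISA to be a poor choice, so it belongs among the sensitivity versions. Every version is post hoc and, like the planned tests, unpaired.

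**Conclusion.** The point holds as a gap in reporting and adjustment. Section 5.7 contains no analysis that is certain to yield a severity-adjusted VWD minus control difference in BOP with a confidence interval, although section 3.2 depends on that quantity. This follows from the retention rule alone. The simulated retention rates only illustrate it and rest on assumed inputs.

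The matching part is an ambiguity between sections 5.1, 5.2 and 5.6. Neither the size nor the direction of any confounding can be derived from the documents, and a claim that the BOP comparison is biased would go beyond them.

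The analysis should be added because it bears on the study's main question and uses data already collected. Confidence is medium, since grade may in fact have been matched.

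**What to change.** 1. Keep the Mann-Whitney test and the stepwise model as planned. Add one supporting linear model for BOP with group and mean PAL-V forced in, the measure being fixed before the model is run. Report the adjusted VWD minus control difference with its 95% CI whatever its p-value.
2. Report three sensitivity versions: mean PPD in place of PAL-V, PISA in place of PAL-V, and PCR added. Label all of these models as added after recruitment ended. If the intervals disagree on whether 5.5 points is excluded, state that the conclusion depends on the adjustment.
3. Tabulate the section 5.6 diagnosis by group, with a row for patients in no listed class, and give the number of pairs with the same diagnosis.
4. Reconcile sections 5.1, 5.2 and 5.6. If grades were not used in matching, claim matching on diagnosis, not on severity.

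**Cost.** No new recruitment or measurement. One or two degrees of freedom are lost and the models carry a post hoc label. At the assumed SD of 7.6, the CI half-width goes from 4.4 points to about 4.6 with one covariate 0.5 SD apart. With two it is 4.6 to 4.9, or 4% to 12% wider for within-group correlations of 0 to 0.5. It is widest when correlated covariates differ in opposite directions. Any BOP variance that the covariates explain would narrow these intervals.
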